1.2.2 Construction and Clinical Validation of the Early Warning System

Construction of the Early Warning System

Expert System Development: Develop an ALI treatment expert system for the entire liver surgery process based on ML models. Integrate clinical guidelines, expert experience, and model predictions to form an ALI early warning system.

Logical Reasoning and Decision-Making Functions: Implement automatic logical reasoning and rapid clinical decision-making based on rules to provide real-time warnings and decision support for clinicians.

System Iteration and Optimization

Application of Information Fusion Technology: Use information fusion technology to integrate multi-source observational data, including vital signs, laboratory results, and imaging data, to enhance the accuracy and reliability of the early warning system.

System Optimization: Refine the early warning system based on clinical feedback and

actual application scenarios to improve system performance and user experience.

Clinical Validation and Evaluation

Expert Concept Validation Tests: Conduct concept validation tests for the iterated early warning system with clinical experts. Evaluate the system's probability predictions and perioperative suggestions, assessing dimensions such as consistency and acceptability through questionnaires.

Clinical Application Validation: Apply the early warning system in clinical practice, collect feedback from clinicians and patients, and evaluate the system's clinical value and effectiveness to further optimize its performance.

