1.2.3 Establishment of an Integrated ALI Diagnosis and Treatment Platform

Theoretical Organization and Requirements Analysis

Theoretical Organization: Organize theories on the entire-process ALI early warning system, perioperative ALI diagnosis and treatment guidelines, expert consensus, case quality control, and knowledge retrieval needs in major liver surgery. Clarify the platform's functional positioning and construction goals.

Requirements Analysis: Communicate with clinicians, nurses, and managers to understand their actual needs and pain points in ALI diagnosis and treatment. This will provide a basis for platform design and development.

Data Center Construction and System Integration

Data Center Establishment: Establish a comprehensive data center for liver surgery wards to collect and integrate clinical, imaging, and laboratory data, providing data support for the platform.

Integration Interface Development: Develop integration interfaces to connect the entire-process ALI early warning platform and knowledge retrieval platform, enabling data sharing and interaction within a unified information system.

User Interface Design and Development

Interface Design: Create an intuitive and user-friendly interface with a simple and clear design style to facilitate quick adoption and operation by medical staff.

Function Implementation: Ensure medical staff can seamlessly access and operate all functions of the integrated system, including patient information queries, early warning result viewing, diagnosis guideline consultation, and knowledge retrieval.

System Testing and Optimization

Supervised Mode Testing: Conduct system testing and optimization in supervised mode with participation from clinicians and nurses. Comprehensive evaluation and feedback will be used to identify and resolve issues promptly.

Enhancing Safety and Effectiveness: Improve the safety and effectiveness of the entire-process ALI diagnosis and treatment platform through testing and optimization. Refine privacy protection mechanisms to ensure patient data security and privacy.

Training and Promotion

Comprehensive Training: Provide comprehensive training for medical staff, covering platform functions, operation methods, and clinical application cases, to ensure proficient use of the new system.

Application Promotion: Effectively implement the entire-process ALI diagnosis and treatment platform in practice. Enhance its adoption through promotion and demonstration,

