2.1 Study Design

This single – center cohort study has two phases: retrospective and prospective.

The retrospective phase analyzed patient data from June 2019 to May 2024 to develop and validate machine learning models. The prospective phase, starting December 2025, will enroll eligible patients. It will collect preoperative, intraoperative, and postoperative data, including cardiopulmonary interaction parameters and clinical blood samples. This data will assess the model's and early warning system's accuracy and effectiveness.

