2.3 Sample Size and Calculation

This study will enroll 2,497 patients to ensure adequate statistical power for external model validation. In major liver surgery, ALI incidence is approximately 4.1%.

Performance Indicator	Hypothetical Value	Target 95% Confidence Interval Width (Corresponding Standard Error)	Sample Size: Number of Study Participants (Events) Required
-----------------------	--------------------	---	---

O/E	1	1 (0.245a)	390 (16)
Calibration Slope	1	0.2 (0.051)	2497 (103)
C-index	0.8	0.1 (0.0255)	1912 (79)
Standardized Net Benefit	0.53	0.2 (0.051)	2403 (99)

Assuming the linear predictor follows a skewed normal distribution, with an outcome event rate of 0.041. The required sample sizes, based on different model performance metrics, are shown above.

In summary, the minimum clinical sample size required for external model validation is 2,497 participants.

2.4 Inclusion Criteria:

- a. Aged ≥ 18 years; b. Scheduled for major liver surgery (e.g., resection of two or more liver segments, liver transplantation); c. Willing to participate and sign the informed consent form.

2.5 Exclusion Criteria:

- a. Patient refusal;
- b. Presence of comorbidities that may affect outcome assessment; c
- c. Incomplete recording of outcome measures;
- d. Failure to follow up postoperatively;
- e. Treating physician's judgment that the patient is unsuitable for inclusion;
- f. Participation in another study that may interfere with outcome assessment of this study.

2.6 Intervention Methods:

This study involves no therapeutic interventions for participants; only their clinical data and samples will be collected.

[figure not shown]

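### The protocol does not settle whether clinicians treating the 2,497 validation patients see live warnings, or which version of the warning system is assessed: sections 1.2.2 and 2.1 point one way, section 2.6 the other

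*Protocol*

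**What the plan says.** - **Section 2.6, Intervention Methods:** "This study involves no therapeutic interventions for participants; only their clinical data and samples will be collected".
- **Section 1.2.2, early warning system:** the rule-based functions are meant to "provide real-time warnings and decision support for clinicians". The system optimization item is to "Refine the early warning system based on clinical feedback and" experience from actual use. The clinical application item is to "Apply the early warning system in clinical practice, collect feedback from clinicians and patients", and to evaluate the system's "clinical value and effectiveness to further optimize its performance".
- **Section 1.2.3, platform:** "Ensure medical staff can seamlessly access and operate all functions of the integrated system, including patient information queries, early warning result viewing". It also plans to put the platform into practice.
- **Section 2.1, Study Design:** the single-centre "cohort study has two phases: retrospective and prospective". "The prospective phase, starting December 2025, will enroll eligible patients", and its data are to assess accuracy and effectiveness for both the model and the warning system.
- **Section 2.3:** 2,497 patients are enrolled for external validation of the model, with targets for O/E, calibration slope, C-index and standardized net benefit.

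**The concern.** Section 2.6 restricts the study to collecting data and samples. Using a live system, gathering clinician and patient feedback on it and improving it from the results goes beyond that. The conflict is with the word *only* in section 2.6. It is not with the absence of therapeutic interventions, because a warning assigns no treatment.

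The statistical stake is the meaning of the validation measures. The primary outcome is ALI within 7 postoperative days, and the platform is built to reduce ALI. If treating clinicians see predictions, they may prevent ALI in flagged patients, so that correct high-risk predictions look like false positives. They may also image and sample flagged patients more often, and so find more ALI under the Berlin criteria. Either way, observed outcomes depend partly on the predictions being tested, and a larger sample does not remove this. If the system changes while patients accrue, its assessment also does not refer to one defined version.

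**Working it through.** **1. The passages side by side.**

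| Question | Section 2.6 | Sections 1.2.2 and 1.2.3 | Section 2.1 |
|---|---|---|---|
| Is live output used? | Data and samples only | Real-time warnings, used in practice and viewable by staff | Not stated |
| In which patients? | Participants get none, if read literally | Not stated | One prospective phase serves both model and system |
| Which version? | Not stated | System refined before and after use in practice | Not stated |

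The nearest thing to a safeguard in section 1.2.3 is supervised-mode testing. It does not say that output is hidden, that the patients are separate or that a version is frozen.

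**2. The plan's own figures (section 2.3).**
- O/E: n = (1 − p)/(p × SE²) = 0.959/(0.041 × 0.245²) = 389.7, so 390 as stated.
- C-index 0.8, SE 0.0255 (Newcombe formula): 1,914 against the stated 1,912.
- Events: 2,497 × 0.041 = 102.4, stated as 103.
- Calibration slope: an SE of 0.051 needs about 8,600 patients with a normal linear predictor, not 2,497. The protocol assumes a skewed normal but gives no shape; shapes from −10 to 10 give 7,121 to 13,423. That is a separate matter. It bears here only on the choice of yardstick in step 4.

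**3. Illustration of what visible output could do.** From the protocol: event rate 0.041 and C = 0.80. Assumed: a correct model, a normal linear predictor (mean −3.811, SD 1.242), warnings for the top 20% of predicted risk, and the effect of those warnings. The flagged group then holds 61% of ALI. If its risk is multiplied by (1 − a):
- O/E = 1 − 0.61a. For a = 0.30 this is 1 − 0.183 = 0.82. For 20% more ALI found (a = −0.20) it is 1 + 0.122 = 1.12.
- The slope is the logistic regression coefficient of the altered outcome on the linear predictor, and C is the concordance recomputed with the altered risks.

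| Assumed effect in the top 20% | O/E | Slope | C |
|---|---|---|---|
| None | 1.00 | 1.00 | 0.800 |
| 10% averted | 0.94 | 0.95 | 0.790 |
| 20% averted | 0.88 | 0.90 | 0.778 |
| 30% averted | 0.82 | 0.84 | 0.765 |
| 50% averted | 0.69 | 0.71 | 0.732 |
| 20% more found | 1.12 | 1.09 | 0.818 |

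At 30% averted, flagging 10% of patients gives 0.87, 0.85 and 0.772; flagging 40% gives 0.76, 0.87 and 0.768.

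**4. Against sampling error at N = 2,497 (same predictor).**
- O/E: SE of ln(O/E) = √(0.959/102.4) = 0.097, so a 95% CI around 1 of 0.83 to 1.21.
- Slope: SE 0.0946, half-width 1.96 × 0.0946 = 0.185.
- C: SE 0.0223, half-width 1.96 × 0.0223 = 0.044.

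At 10% averted, and at 20% more found, every shift stays inside these limits. At 30% averted, O/E (0.82) just passes its limit, while the slope shift (0.16) and the C shift (0.035) do not. In 3,000 simulated samples per setting, a correct model's CI lay wholly below 1 in 3% (slope) and 1% (O/E) with nothing averted, and in 38% and 46% with 30% averted.

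The protocol's own targets give a different picture by measure. The stated slope half-width of 0.1 is reached at about 20% averted. The wide O/E target, exp(±1.96 × 0.245) = 0.62 to 1.62, is left only at 62% averted.

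**The case against.** **Section 2.6 is itself a safeguard.** If it is strict enough to conflict with live use, it is strict enough to keep live use away from participants. This stands in part. It would be wrong to say that no passage bears on the separation. But the safeguard is only implicit, and section 1.2.2 includes feedback from patients while section 2.1 assesses the system in the same prospective phase.

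**Section 1.2 may describe a wider programme.** It includes a data centre, interface design, training and promotion, which are not cohort procedures, and section 2 lists no live-use step. Assessing a system does not require showing its output. This is a fair reading, but the text does not state it and gives live use no patient set of its own.

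**The missing figures may fix the sequence.** This stands. A reader might infer that the 2,497 will be treated by clinicians who see warnings; the documents do not say so.

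**The model may be stable.** This stands. A reader might infer that the machine learning model is refitted during accrual. Section 2.1 places model development in the retrospective phase, and the refinement in section 1.2.2 is of the warning system. The version problem is shown for the system, not for the model to which the O/E, slope and C targets apply.

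**The bias need not run against the model.** This stands. That inference holds only if averted cases dominate; extra ascertainment works the other way and can offset it.

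**This belongs in the SAP.** It does not. An SAP can name the version analysed, but whether clinicians see predictions is a matter of study conduct, to be fixed before the prospective phase.

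**Conclusion.** The concern holds as a conflict to be reconciled, not as proof of contamination. Live application, feedback and continued optimization do not fit a study limited to data and samples. The visible text leaves open whether clinicians treating the 2,497 see predictions and which system version is assessed. If output is visible, the validation measures no longer describe the model alone, and the sign of the distortion is not known in advance.

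The size is illustrative. The documents give neither a flagged share nor an effect of warnings. Under the assumptions shown, a small effect is lost in sampling error, and averting about 30% of ALI in flagged patients shifts results by roughly the sampling uncertainty at 2,497. The conflict itself depends neither on these figures nor on the sample-size table. If predictions are hidden from the treating team, the problem does not arise.

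Separately, section 2.1 speaks of effectiveness, but no comparator is described. The design can support conclusions on predictive accuracy, net benefit and acceptability, not on reduced ALI incidence.

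**What to change.** 1. Reconcile sections 1.2.2, 1.2.3, 2.1 and 2.6, and say whether live application belongs to this cohort.
2. Lock the model, and the system version to be assessed, before prospective validation starts.
3. Compute predictions for the 2,497 without showing them to the treating team. Place live application and refinement after that set, or outside it.
4. Amend section 2.6 to cover the live and feedback step.
5. State that, without a comparator, conclusions are limited to predictive accuracy, net benefit and acceptability.
6. If a figure already fixes this sequence, put it into the text of sections 2.1 and 2.6.

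**Cost:** changes to wording and sequencing, and later live use at this single centre. The delay cannot be estimated because no accrual rate is given. Concurrent live use in other patients would shorten it but could still influence the same clinicians, so live use after the validation set is cleaner.

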1.2.3 Establishment of an Integrated ALI Diagnosis and Treatment Platform

Theoretical Organization and Requirements Analysis

Theoretical Organization: Organize theories on the entire-process ALI early warning system, perioperative ALI diagnosis and treatment guidelines, expert consensus, case quality control, and knowledge retrieval needs in major liver surgery. Clarify the platform's functional positioning and construction goals.

Requirements Analysis: Communicate with clinicians, nurses, and managers to understand their actual needs and pain points in ALI diagnosis and treatment. This will provide a basis for platform design and development.

Data Center Construction and System Integration

Data Center Establishment: Establish a comprehensive data center for liver surgery wards to collect and integrate clinical, imaging, and laboratory data, providing data support for the platform.

Integration Interface Development: Develop integration interfaces to connect the entire-process ALI early warning platform and knowledge retrieval platform, enabling data sharing and interaction within a unified information system.

User Interface Design and Development

Interface Design: Create an intuitive and user-friendly interface with a simple and clear design style to facilitate quick adoption and operation by medical staff.

Function Implementation: Ensure medical staff can seamlessly access and operate all functions of the integrated system, including patient information queries, early warning result viewing, diagnosis guideline consultation, and knowledge retrieval.

System Testing and Optimization

Supervised Mode Testing: Conduct system testing and optimization in supervised mode with participation from clinicians and nurses. Comprehensive evaluation and feedback will be used to identify and resolve issues promptly.

Enhancing Safety and Effectiveness: Improve the safety and effectiveness of the entire-process ALI diagnosis and treatment platform through testing and optimization. Refine privacy protection mechanisms to ensure patient data security and privacy.

Training and Promotion

Comprehensive Training: Provide comprehensive training for medical staff, covering platform functions, operation methods, and clinical application cases, to ensure proficient use of the new system.

Application Promotion: Effectively implement the entire-process ALI diagnosis and treatment platform in practice. Enhance its adoption through promotion and demonstration,

offering robust support for the clinical management of liver surgery patients.

2. Research Protocol

2.1 Study Design

This single – center cohort study has two phases: retrospective and prospective.

The retrospective phase analyzed patient data from June 2019 to May 2024 to develop and validate machine learning models. The prospective phase, starting December 2025, will enroll eligible patients. It will collect preoperative, intraoperative, and postoperative data, including cardiopulmonary interaction parameters and clinical blood samples. This data will assess the model's and early warning system's accuracy and effectiveness.

2.2 Study Population

Inclusion criteria: Patients aged ≥ 18 years undergoing major liver surgery (e.g., resection of two or more liver segments, liver transplantation). Exclusion criteria: Patients declining participation, having comorbidities affecting outcome assessment, or having incomplete data records.

2.3 Sample Size and Calculation

This study will enroll 2,497 patients to ensure adequate statistical power for external model validation. In major liver surgery, ALI incidence is approximately 4.1%.

Performance Indicator	Hypothetical Value	Target 95% Confidence Interval Width (Corresponding Standard Error)	Sample Size: Number of Study Participants (Events) Required
-----------------------	--------------------	---	---

O/E	1	1 (0.245a)	390 (16)
Calibration Slope	1	0.2 (0.051)	2497 (103)
C-index	0.8	0.1 (0.0255)	1912 (79)
Standardized Net Benefit	0.53	0.2 (0.051)	2403 (99)

Assuming the linear predictor follows a skewed normal distribution, with an outcome event rate of 0.041. The required sample sizes, based on different model performance metrics, are shown above.

In summary, the minimum clinical sample size required for external model validation is 2,497 participants.

2.4 Inclusion Criteria:

- a. Aged ≥ 18 years; b. Scheduled for major liver surgery (e.g., resection of two or more liver segments, liver transplantation); c. Willing to participate and sign the informed consent form.

2.5 Exclusion Criteria:

- a. Patient refusal;
- b. Presence of comorbidities that may affect outcome assessment; c
- c. Incomplete recording of outcome measures;
- d. Failure to follow up postoperatively;
- e. Treating physician's judgment that the patient is unsuitable for inclusion;
- f. Participation in another study that may interfere with outcome assessment of this study.

2.6 Intervention Methods:

This study involves no therapeutic interventions for participants; only their clinical data and samples will be collected.

[figure not shown]

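### Section 2.3 uses 2,497 as both the number enrolled and the minimum needed for validation, although 2.5c and 2.5d remove patients after enrolment and no allowance for loss is stated

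*Protocol*

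**What the plan says.** Section 2.3 opens with "This study will enroll 2,497 patients to ensure adequate statistical power for external model validation" and ends by stating that "the minimum clinical sample size required for external model validation is 2,497 participants". The figure is the largest of four in its table:

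- calibration slope: 2,497 participants (103 events), CI width 0.2, standard error (SE) 0.051
- standardized net benefit: 2,403 (99 events), width 0.2, SE 0.051
- C-index of 0.8: 1,912 (79 events), width 0.1, SE 0.0255
- O/E: 390 (16 events), width 1, SE 0.245

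The stated basis is "Assuming the linear predictor follows a skewed normal distribution, with an outcome event rate of 0.041".

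Under 2.4, patients enter when surgery is scheduled and consent is signed. Section 2.5 then excludes for "Incomplete recording of outcome measures" (item c) and "Failure to follow up postoperatively" (item d). Section 2.2 words its data criterion more broadly: patients declining, with interfering comorbidities, "or having incomplete data records". Follow-up (2.7) and the primary outcome (section 4) cover the seven days after surgery. The protocol gives no expected loss rate, inflation or replacement rule.

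**The concern.** The table gives the number that must contribute to the validation analysis. A patient with no recorded outcome adds nothing to a calibration slope, a net benefit, a C-index or an O/E ratio. The opening sentence of 2.3 uses that same number for recruitment. The two uses agree only if nobody is lost after enrolment, yet 2.5c and 2.5d provide for exactly such losses.

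At stake is whether the protocol's stated precision is what the completed study would report. The slope row alone sets the sample size and has no slack. The next row, net benefit, has 94 patients of slack.

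**Working it through.** **Inputs.** All come from the table and text of 2.3, except the loss rate d. The protocol gives no loss rate, so d is assumed over a range.

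**Step 1: the plan's own figures.**

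- O/E: n = (1 − φ)/(φ·SE²) = 0.959/(0.041 × 0.245²) = 389.7, so 390. This matches.
- C-index: Newcombe's standard error with C = 0.8 and φ = 0.041 gives SE 0.02551 at n = 1,912. Solving for SE 0.0255 gives 1,914 against 1,912 stated, which agrees within rounding.
- Events: 0.041 × 2,497 = 102.4, 0.041 × 2,403 = 98.5 and 0.041 × 1,912 = 78.4. Rounded up, these are the stated 103, 99 and 79.
- Width to SE: 0.2/(2 × 1.96) = 0.051. This matches.
- Calibration slope: SE² = I_a/[n(I_a·I_b − I_ab²)], where the I terms are the average information for intercept, slope and their cross-term. They depend on the distribution of the linear predictor, whose parameters the protocol does not give, so 2,497 cannot be reproduced directly. I set C = 0.8 and φ = 0.041 and tried normal and skew-normal predictors (shape −5 to 8). SE 0.051 then needed about 7,100 to 11,900 participants (8,560 for the normal). For those predictors the width at 2,497 would be 0.2 × √(7,115/2,497) = 0.34 up to 0.2 × √(11,906/2,497) = 0.44, before any loss.

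**Step 2: when each target is missed.**

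- Slope: at any d > 0, because 2,497(1 − d) < 2,497.
- Net benefit: at d > 1 − 2,403/2,497 = 3.8%.
- C-index: at d > 1 − 1,912/2,497 = 23.4%.
- O/E: at d > 1 − 390/2,497 = 84.4%.

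**Step 3: by how much, taking the plan's rows at face value.** N = 2,497(1 − d). Slope width = 0.2/√(1 − d). Net-benefit width = 0.2·√(2,403/N).

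| Assumed loss | Analysable N | Events at 4.1% | Slope width (target 0.2) | Net-benefit width (target 0.2) |
|---|---|---|---|---|
| 2% | 2,447 | 100 | 0.202 | 0.198 |
| 5% | 2,372 | 97 | 0.205 | 0.201 |
| 10% | 2,247 | 92 | 0.211 | 0.207 |

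The slope column depends on the row that step 1 could not reproduce. It shows the relative widening (about 1%, 3% and 5%), not the precision to expect.

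**The case against.** The best reply is that 2,497 may already be the evaluable number. Section 2.1 says that the prospective phase takes in eligible patients, and 2.5c and 2.5d are listed as eligibility exclusions. Read literally, a patient who meets either was never eligible and does not count. That reading is open, so a reader should not infer that the stated precision is certain to be missed. But 2.4 admits patients before surgery, and nothing says that those excluded later are uncounted or replaced. The text supports both readings, and that ambiguity needs settling.

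The effect is also small. The outcome window is seven days after major surgery, and nothing in the protocol points to heavy loss. At 2%, only the slope target is missed, by 0.002. This stands, and it limits the weight of the point.

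Three stronger inferences are not supported:

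- **That 2.2 removes prospective patients for any missing predictor.** Section 2.2 names no phase and may mainly describe the retrospective records. The point rests on 2.5c and 2.5d without it.
- **That imputing predictors would close the gap.** Items 2.5c and 2.5d concern outcomes and follow-up, which predictor imputation does not restore.
- **That 2,497 is proven wrong by a factor of three or more.** Step 1 shows that it does not follow from the predictors tried. The parameters actually used are not stated, so the row is unverified, not refuted.

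**Conclusion.** The point holds in limited form. As written, 2.3 makes one number serve for both enrolment and analysis, while 2.5c and 2.5d allow patients to drop out between the two. Any loss takes the analysed number below the plan's own minimum. The slope target then fails at once and the net-benefit target above 3.8% loss; the C-index and O/E targets are safe at plausible losses.

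The size is modest: a slope width of about 0.202 to 0.211 against 0.2 for losses of 2% to 10%. This rests on two things the protocol does not settle: the loss rate, which is assumed, and the SE of 0.051 at 2,497, which is taken at face value. If the sponsor meant 2,497 as the evaluable number, the gap closes once the text says so.

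**What to change.** 1. Check the basis of the calibration-slope row first, and state the linear-predictor parameters behind it. Restate no width until this is done.
2. In 2.3, choose one of two wordings:
   - State that 2,497 is the number with an assessable day-7 outcome. Patients excluded under 2.5c or 2.5d then do not count toward it, so the number consented would exceed 2,497 by the losses: 2,497/(1 − d) is 2,548 at 2%, 2,629 at 5% and 2,775 at 10%.
   - Keep 2,497 as enrolment, and state the analysable number and expected CI widths at an exclusion rate taken from the retrospective records. This adds no patients.
3. Reconcile the data-completeness exclusion in 2.2 with 2.5c, and say which phase each governs.

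The cost is a few sentences in 2.2 and 2.3 and a look at the retrospective records. Neither wording raises the planned figure of 2,497. Under the second, the stated precision becomes slightly less favourable.

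### The calibration-slope row that sets enrolment is not attainable: at 4.1% events, 2,497 patients cannot give a slope 95% CI width of 0.2

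*Protocol*

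**What the plan says.** Protocol section 2.3 sizes the study on the precision of four performance measures. Its stated basis is: "Assuming the linear predictor follows a skewed normal distribution, with an outcome event rate of 0.041". No mean, SD or skewness is given for the linear predictor (LP). The table reads:

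| Measure | Assumed value | Target 95% CI width (SE) | Patients (events) |
|---|---|---|---|
| O/E | 1 | 1 (0.245) | 390 (16) |
| Calibration slope | 1 | 0.2 (0.051) | 2,497 (103) |
| C-index | 0.8 | 0.1 (0.0255) | 1,912 (79) |
| Standardized net benefit | 0.53 | 0.2 (0.051) | 2,403 (99) |

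The slope row is the largest, and the section takes its conclusion from it: "the minimum clinical sample size required for external model validation is 2,497 participants". The same number is the enrolment commitment: "This study will enroll 2,497 patients to ensure adequate statistical power for external model validation".

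**The concern.** The precision of a calibration slope depends on the number of events and on how widely the LP is spread among patients whose risk is not close to 0 or 1. With 103 events, an SE of 0.051 asks for a very wide spread. A wide spread combined with a mean risk of only 4.1% pushes most patients towards zero risk, where they say little about the slope. The row therefore looked too optimistic for its own event rate.

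This row alone makes the minimum 2,497 rather than 2,403. If it is wrong, the protocol promises a precision that the design does not deliver on the criterion that fixes the sample size. For example, an interval of about 0.81 to 1.19 supports a much weaker statement about calibration than one of 0.9 to 1.1.

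**Working it through.** **Inputs.** From section 2.3: event rate φ = 0.041, skew-normal LP, true slope 1, SE 0.051 (0.2 / 3.92 = 0.051). Assumption: C = 0.8, taken from the C-index row, because the LP's SD is not stated. It is varied and then dropped below.

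**1. The neighbouring rows.**
- O/E: n = (1 − φ) / (φ × SE²) = 0.959 / (0.041 × 0.245²) = 389.7. Printed: 390.
- C-index: SE² = C(1 − C)[1 + (n/2 − 1)(1 − C)/(2 − C) + (n/2 − 1)C/(1 + C)] / [n²φ(1 − φ)]. With C = 0.8 and SE 0.0255, n is about 1,913. Printed: 1,912.
- Net benefit: no risk threshold is given, so one was solved to return 0.53 at C = 0.8. This gives 2,259 to 2,273. Printed: 2,403, about 6% away. It is a rough check only.

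**2. The slope formula.** n = I_a / [SE² (I_a × I_b − I_ab²)], where I_a = E[p(1 − p)], I_ab = E[LP p(1 − p)], I_b = E[LP² p(1 − p)]. Equivalently, n = 1 / (SE² × I_a × V), where V is the variance of the LP weighted by p(1 − p). The LP mean is solved so that E[p] = 0.041.

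**3. Normal LP, C = 0.8.** This needs mean −3.81 and SD 1.24. Integration gives I_a = 0.03613 and a weighted SD of 1.1128, so V = 1.2384. Then n = 1 / (0.002601 × 0.03613 × 1.2384), which is 8,594 before rounding. At 2,497 the SE is 0.051 × √(8,594 / 2,497) = 0.095, a width of 0.37.

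**4. Full skew-normal range, C = 0.8.**

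| Skewness | n for SE 0.051 | SE at 2,497 | Width at 2,497 |
|---|---|---|---|
| −0.995 | 14,363 | 0.122 | 0.48 |
| −0.78 | 11,317 | 0.109 | 0.43 |
| −0.51 | 9,855 | 0.101 | 0.40 |
| 0 | 8,594 | 0.095 | 0.37 |
| +0.51 | 7,591 | 0.089 | 0.35 |
| +0.995 | 7,100 | 0.086 | 0.34 |

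The required n is 2.8 to 5.8 times the printed one.

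**5. Other values of C.** At C = 0.75, n is 9,812 to 18,432 (width at 2,497: 0.40 to 0.54). At C = 0.85, n is 5,639 to 11,897 (0.30 to 0.44).

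**6. C left free.** Choosing the most favourable SD for each shape, the smallest n is 5,790 (skewness −0.51), 5,366 (0), 4,986 (+0.51) and 4,830 (+0.995, where C = 0.92). The last gives a width of 0.278 at 2,497.

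**7. A hand check.** I_a cannot exceed 0.041 × 0.959, so n × I_a is at most 2,497 × 0.041 × 0.959 = 98.2. SE 0.051 then needs a weighted LP SD of at least 1 / (0.051 × √98.2) = 1.98. At C = 0.8 it is 0.85 to 1.24.

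**8. Any LP shape at all.** A linear-programming bound over every distribution with mean risk 0.041 gives n of at least about 2,741.

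**9. Simulation.** Logistic recalibration at n = 2,497 and C = 0.8, 400 replicates per shape, gave mean widths of 0.486 (skewness −0.99), 0.402 (−0.51), 0.374 (0) and 0.340 (+0.99). The narrowest of all 1,600 was 0.298. The data come from the same model, so this confirms the formula, not the inputs.

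**10. Where 2,497 might come from.** Two back-fitted possibilities, neither provable from the document:
- An LP not tied to 4.1%. A normal LP with mean −2.78 and SD 2 gives 2,501, but implies 14.8% events (368), against the 103 printed.
- A target width of 0.4 (SE 0.102). At 4.1% events and C = 0.8, a skewness of about −0.54 with SD about 1.45 gives 2,497, but this contradicts the printed width and SE.

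**The case against.** Four points can be made for the protocol.

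- **The missing LP parameters might rescue the row.** The protocol does not say that C = 0.8 applies to the slope row. The 4,830 floor also belongs to the skew-normal family: heavier-tailed skewed shapes that were tried bring it down to about 4,200. This stands as a limit on the size of the error, but not on its existence, because the bound over all shapes (about 2,741) is still above 2,497.
- **The printed 0.2 may be a half-width.** At C = 0.8 that needs 7,100 / 4 = 1,775 to 14,363 / 4 = 3,591 patients, a range that contains 2,497, and it keeps the 4.1% rate and the 103 events. It is the most charitable reading. However, the column is headed as a full width and the SE of 0.051 matches a full width, so the row is still wrong as printed.
- **Another model might have been used.** Treating the intercept as known gives about 1,320 to 1,410 at C = 0.8, which is not 2,497 either.
- **The consequence is small.** The study is observational, no decision rule in the protocol depends on the slope interval, and without this row the minimum falls by only 2,497 − 2,403 = 94 patients. This is fair, and it is a reason to keep the remedy light. It does not justify leaving a false precision statement as the basis for enrolment.

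The net-benefit row is not truly reproduced, so confidence in the rest of the table rests mainly on the O/E and C-index rows.

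**Conclusion.** The concern holds. The slope row contradicts the event rate and LP family stated beside it. For a skew-normal LP with 4.1% events and a true slope of 1, the target needs at least about 4,830 patients at any C-index. If C = 0.8 is assumed, it needs about 7,100 to 14,400. With 2,497 patients the interval will be about 1.7 to 2.4 times as wide as stated at C = 0.8, and at least about 1.4 times as wide for any C. No single correct n can be given, because the LP's mean, SD and skewness are not stated, and the cause of the error cannot be settled from the document. The row should be corrected because it is the one that fixes the sample size. The printed sizes for O/E, C-index and net benefit all lie below 2,497.

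**What to change.** In section 2.3:

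1. State the mean, SD and skewness of the assumed LP, and confirm that they give a 4.1% event rate.
2. Recompute the slope row from those inputs. Replace the printed width and SE with what 2,497 patients deliver. The sponsor's own inputs should set the figure; if C = 0.8 it will lie at about 0.34 to 0.48 (SE about 0.086 to 0.122).
3. Remove the claim that 2,497 gives a slope width of 0.2. Reword the closing sentence so that 2,497 is the planned size with its expected precision on each measure.

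This costs wording and one table row, and the stated precision for the slope becomes less favourable. Enrolment need not change. If the sponsor prefers to keep a width of 0.2, the sample size has to change instead, to at least about 4,800, which roughly doubles enrolment at the minimum.
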